3. INR > 1.5
4. Patients with uncorrectable coagulopathy.
5. Currently breastfeeding or pregnant (latter confirmed by serum pregnancy test).
6. Physical or psychological condition which would impair study participation.
7. ASA (American Society of Anesthesiologists) score of > 4.
8. Any other loco-regional therapies at the target lesion(s) within 30 days of the ablation procedure.

NUMBER OF PARTICIPANTS

Preliminary retrospective data on the control arm suggest that a minimum ablation margin (MAM) of 2mm (SD 2) is generally achieved when ablation is performed without the use of software guidance. A sample size of 50 evaluable subjects in each group will have 80% power to detect a difference in means of -1.132 (the difference between a control arm mean, of 2 mm and the experimental arm mean of 3.132) assuming that the common

standard deviation is 2 using a two group t-test with a two-sided 0.05 significance level.

Assuming an accrual rate of 35 patients per year, the study accrual duration will be around 3 years, with follow-up for at least 2 years, totaling 5 years for the entire study duration. We will have an interim look for superiority once half the evaluable subjects (n=50) have been enrolled. A Lan-Demets spending function using an Obrien-Flemming boundary will be used for superiority stopping boundaries. We will stop enrollment at the control arm at our interim look if our p-value is less than 0.003. East v6.5 was used for sample size calculation. The next 50 patients would be enrolled on the experimental arm only to allow further development of the proposed biomechanical model on clinical practice, as well allow other interventional radiologists at our Department to utilize it.

We plan to screen 140 subjects and expect approximately 20 subjects to be screen failures. Furthermore, subjects after randomization who drop out due to tumor progression, inability to clearly depict target lesions, and major complications precluding further ablation will be considered inevaluable. To account for an expected 20% inevaluable subjects, we will enroll a total of 120 subjects to ensure 100 evaluable subjects.

STUDY PLAN/DESIGN

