Statistical analysis of this study will be the responsibility of the principal investigator (PI) and statistician. The PI and statistician will also be responsible for the appropriate conduct of an internal review for the final dataset and any study-related material to be authorized for publication.

To assess the effect of applying biomechanical image registration models during percutaneous microwave ablation, the primary endpoint of this intent-to-treat randomized trial will be on the impact of the software use on the minimal margins of ablated lesions properly covered by ablation on a three-dimensional analysis. Patients will be evenly randomized (i.e., 1:1 ratio) to two treatment arms (i.e. experimental arm - including anatomical modeling of the liver, and control arm) using the Pocock-Simon dynamic allocation method to balance the baseline covariates: tumor histology

(colorectal vs other histologies), RAS mutation (for colorectal only, yes vs. no vs.

undetermined), lesion size (<2cm, 2.0-3.0cm, >3cm-<5cm), subcapsular location, defined as tumor within 1 cm from the liver capsule (yes vs no) and presence of multiple lesions (yes vs. no). At the end of the study, the average minimum ablation margins will be compared between two arms using a 2-sample t-test (or Wilcoxon rank-sum test). The means and corresponding 95% confidence intervals will be reported for both arms of the study.

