As a secondary objective, the Kaplan-Meier method will be used to estimate local tumor progression-free survival (LTPFS) and 95% confidence intervals for the quantiles of the LTPFS function based on the method of Brookmeyer and Crowley will be calculate for each arm. Time point probabilities (e.g., 2-year LTPFS) and the associated log-log transformed pointwise 95% confidence will also be reported. A multivariate Cox-proportional hazards model will be fitted to the data with ablative margin as a continuous variable to assess the significance of study arm and ablative margin size on LTPFS while simultaneously adjusting for known covariates that effect LTPFS. LTPFS will be measured from date of ablation to earliest date of progression at the ablated lesion, death. Those progression free and alive will be censored at their date of last clinic visit. Similar analysis will be used for 2-years intra-hepatic (progression at any site of the liver) progression-free survival and overall survival. Standard summary statistics will be computed for complication rates, quality of life, and liver function and compared between arms. Statistical significance will be defined as $p < 0.05$.

B. Randomization

A dynamic randomization method by Pocock and Simon will be used with a minimization probability parameter of 0.90. The randomization process will be controlled to ensure a balanced stratification by treatment arm for the factors listed above. Patients will be randomized to either experimental arm or no control arm using the Clinical Trial Conduct (CTC) website (<https://biostatistics.mdanderson.org/ClinicalTrialConduct>), which is housed on a secure server at MDACC and maintained by the MDACC Department of Biostatistics. Access to the website will be gained through usernames and passwords provided by the MDACC Department of Biostatistics to the clinical team. Training on the use of the CTC website to randomize patients on the study will be provided by the biostatistical collaborators. This is an open-label trial with stratified randomization. When a patient is enrolled on the study, the research nurse or coordinator of the study will enter patient's information including medical record number and stratification factors. Through the web interface, after the randomization button is clicked, the result of the randomization will be displayed on the screen for users to view. All data on randomization will be stored in a secure SQL server database.

PROTOCOL MONITORING PLAN

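### The primary margin test leaves out the five minimisation factors: it is valid, but if they predict the margin alike in both arms it forgoes about 2 points of power at an assumed R² of 0.1 and 5 at 0.2

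*Combined protocol and SAP*

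**What the plan says.** Statistical Methods, A. Analysis Plan, assigns patients 1:1 "using the Pocock-Simon dynamic allocation method to balance the baseline covariates". The factors are histology (colorectal or other), RAS status within colorectal, three lesion-size classes, subcapsular location and multiple lesions. Under B. Randomization, "A dynamic randomization method by Pocock and Simon will be used with a minimization probability parameter of 0.90", and staff enter each patient's "information including medical record number and stratification factors" before allocation.

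The primary analysis uses none of these factors: "the average minimum ablation margins will be compared between two arms using a 2-sample t-test (or Wilcoxon rank-sum test"). No rule chooses between the two tests. For estimation, "The means and corresponding 95% confidence intervals will be reported for both arms of the study"; no interval for the difference is planned. Covariate adjustment appears only in the secondary Cox model for local tumor progression-free survival.

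Number of Participants sizes the trial at 50 evaluable patients per arm for a difference of 1.132 mm, with the "standard deviation is 2 using a two group t-test with a two-sided 0.05 significance level". It adds an interim look at 50 evaluable patients with a threshold of 0.003: "A Lan-Demets spending function using an Obrien-Flemming boundary will be used for superiority stopping boundaries". No final-look level is printed. The Analysis Plan ends with "Statistical significance will be defined as" p < 0.05.

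**The concern.** Minimisation forces the arms to resemble each other on the five factors. If a factor predicts the margin, the observed difference in means then varies less from trial to trial than under simple randomisation. The two-sample t-test does not know this. Its standard error still contains the factor-related variance, so the p-value is too large on average, the type I error falls below 5%, and a t-based interval for the difference is too wide. A model containing the factors removes that variance from the error term.

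The stake is precision from patients already enrolled, not validity. The size depends on how well the factors predict the margin, which the documents do not say. Section 1.4 gives only a qualitative hint: wider margins have been recommended for RAS-mutated tumours. Section 1.8, part B, gives a reason for a weaker link in the experimental arm, where the operator acts on the software's margin reading.

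Three smaller gaps sit in the same text: no interval for the between-arm difference, an open choice of test, and an unstated final significance level.

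**Working it through.** **Inputs from the documents.** 50 evaluable per arm, SD 2 mm, difference 1.132 mm (2 v 3.132), two-sided 0.05; 120 randomised for 100 evaluable; interim p < 0.003 at 50 evaluable; minimisation probability 0.90.

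**Assumed.** R² from 0 to 0.3; normal margins. Simulated prevalences: colorectal 60%; RAS yes/no/undetermined 40/45/15% of colorectal; size classes 40/40/20%; subcapsular 40%; multiple 35%.

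**1. The plan's own figure.** SE = 2 × √(2/50) = 0.400; noncentrality = 1.132/0.400 = 2.83; critical value t(98) = 1.984. Noncentral t power is 80.0%, so the stated 80% reproduces.

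**2. Closed form, with the factors fully balanced and acting alike in both arms.**
- t-test power ≈ Φ[(2.83 − 1.984)/√(1 − R²)]. R² = 0.1: 81.4%. R² = 0.2: 82.8%.
- t-test type I error ≈ 2{1 − Φ[1.96/√(1 − R²)]}. R² = 0.1: 3.9%. R² = 0.2: 2.8%.
- Adjusted model: residual SD = 2√(1 − R²). Parameters: intercept 1, arm 1, RAS in four levels 3, size 2, subcapsular 1, multiple 1, in total 9, so residual df = 91. Power is 83.9% and 87.9%.
- Gain: about 2.6 and 5.1 points. Comparing with the nominal 80% instead would overstate it (about 4 and 8), because minimisation already helps the t-test.

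**3. Simulation.** Pocock-Simon at 0.90, n = 100, 20,000 trials per cell (Monte Carlo SE about 0.15 points for type I error, 0.3 for power). Ranges cover two patterns: all five factors contributing equally, or size and subcapsular location only. Same effect in both arms:

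| R² | t-test type I error | Power, t-test | Power, adjusted | Gain (points) |
|---|---|---|---|---|
| 0 | 5.0–5.2% | 79.5–80.0% | 79.0–79.5% | −0.5 |
| 0.05 | 4.5–4.6% | 80.3–80.9% | 81.5–81.9% | +1.1 |
| 0.1 | 3.8–4.2% | 81.2–81.4% | 83.6% | +2.2 to +2.3 |
| 0.2 | 2.9–3.1% | 82.1–82.5% | 87.5–87.9% | +5.4 |
| 0.3 | 2.1–2.4% | 82.9–83.6% | 91.2–91.5% | about +8 |

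At R² = 0.1 the t-test's mean standard error is 0.399 against a true SD of 0.380–0.384, which is the mechanism described above. The adjusted model's type I error is 4.8–5.2% in every cell. The 95% half-width for the difference is 0.79 mm unadjusted, against 0.76 (R² = 0.1) and 0.71 (R² = 0.2) adjusted.

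Weaker link in the experimental arm, gain at control-arm R² of 0.1 / 0.2 / 0.3:
- half strength: +0.9 to +1.3 / +2.6 to +2.9 / +4.6;
- control arm only: +0.2 to +0.3 / +0.8 to +1.1 / +1.6 to +2.0.

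**4. 120 randomised, 100 evaluable at random** (equal effects). Gains are −0.9, +2.6 and +5.5 points at R² = 0, 0.1 and 0.2. The t-test's type I error is 5.1%, 4.4% and 3.7%.

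**5. Choice of test.** In the worst case, taking the smaller of the t-test and Wilcoxon p-values, type I error is 5.8% at R² = 0 and 4.8% at R² = 0.1.

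**6. Two looks.** The O'Brien-Fleming-type spending function at half the information gives 0.0031 then 0.0490, which agrees with the printed 0.003. By bivariate normal, 0.003 then 0.05 spends 0.0510; 0.003 then 0.049 spends 0.0500. At information 0.4 and 0.6 the pairs are 0.0008/0.0497 and 0.0076/0.0476. The adjusted model at both looks, with 0.003 then 0.049, has overall type I error 4.9–5.1%. Chance of crossing at the interim under the planned effect, t-test v adjusted: 14.7 v 13.5% (R² = 0), 13.5 v 15.7% (0.1), 12.8 v 19.3% (0.2).

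**The case against.** The plan's test is valid and adequately powered, so adjustment is optional, and its benefit rests on an R² that the documents do not supply. They also give grounds to expect a small one. Section 1.4 ties lesion size, number and location to local control, and RAS to recurrence and survival, not to the margin achieved. Section 1.8 applies one margin cut-off whatever the RAS status. Inclusion criterion 2 in section 1.6 admits only tumours judged coverable with a 5 mm margin, which may weaken the link in both arms. If the factors act only in the control arm the gain is close to nil. A small check of that case (2,500 trials per cell, 120 randomised, adjusted model at 0.049 v t-test at 0.05) showed none: 79.7 v 80.5% at R² = 0.1 and 79.7 v 79.9% at R² = 0.2.

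Nine parameters are also many for 50 patients. The RAS-undetermined level would average 50 × 0.60 × 0.15 = 4.5 patients, with two or fewer in 16% of trials. If undetermined were 5% of colorectal, the level would be empty in 0.97^50 = 22%. Finally, naming the spending function already fixes the final level in principle, and the excess is only 0.051 against 0.050.

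All of this stands as a limit on size. It does not remove the point: the downside is under one point of power at the final look, the upside is several points if the factors matter, and sparse levels need only a collapsing rule.

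**Conclusion.** The point holds as an improvement to consider, not as a defect. The unadjusted test controls type I error and has its stated power. Relative to a model with the minimisation factors, it forgoes about 2 points of power at R² = 0.1, about 5 at R² = 0.2 and about 8 at R² = 0.3, provided the factors act alike in both arms. It forgoes 0 to 2 points if they act only in the control arm, and nothing at R² = 0. These figures rest on assumed R² values and factor prevalences, normal margins and SD 2 mm in each arm. Confidence in the size is therefore medium. The missing interval for the difference, the open choice of test and the unprinted final level are minor gaps whatever R² is.

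**What to change.** Before any comparison by arm is seen, which matters because the trial is open-label, amend the Analysis Plan as follows.

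- **Primary analysis:** a single linear model of minimum ablation margin on arm plus the factors as coded for allocation. Enter RAS as one four-level factor (not colorectal, yes, no, undetermined), which absorbs histology; then size class, subcapsular location and multiplicity.
- **Both looks:** use the same model at the interim and final looks, with a pre-stated rule for collapsing sparse RAS levels. State which patients enter the final model if control-arm enrolment stops at the interim.
- **Estimate:** report the adjusted between-arm difference with its confidence interval.
- **Sensitivity:** name the unadjusted t-test and the Wilcoxon test as sensitivity analyses, which closes the choice between them.
- **Final level:** print 0.049 two-sided if the interim falls at half the information; otherwise recompute it from the spending function.

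The cost is SAP wording, since the factors are already recorded. The model uses seven degrees of freedom (residual 91 instead of 98; 41 instead of 48 at the interim). If the factors explain nothing, final power falls by 0.5 to 0.9 points; with 100 randomised, the loss is 0.7–0.8 when the model is tested at 0.049 against a t-test at 0.05. The chance of crossing at the interim falls by about 1 point.

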1.2 Secondary Objectives

1. To assess whether applying the proposed method during percutaneous ablation improves local tumor progression-free survival (LTPFS) rates;
2. Evaluate impact of software use on procedure workflow;
3. Impact of software use on complication rates, quality of life, liver function;
4. Evaluate oncological outcomes (intra-hepatic and overall progression-free survivals, and overall survival)

BACKGROUND

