1.4 Clinical Impact

Among the local therapies utilized for liver cancers, percutaneous thermal ablation has become a widely utilized option for patients not eligible for surgery, with most recent series demonstrating similar 5-year overall survival rates between surgery and ablation

(5-7). This highlights the efficacy of this treatment modality on prolonging OS in patients with liver cancers (4).

In order to achieve optimal results with ablation, low rates of local recurrence (also known as *local tumor progression* [LTP]) at the treated tumors should be obtained. More recently, results of a prospective randomized phase II trial demonstrated that patients with CLM treated liver ablation in association with systemic chemotherapy had significantly longer overall survival rates (OS) when compared to patients treated only with systemic chemotherapy (4), emphasizing the role of aggressive local treatment on prolonging OS in patients with unresectable CLM. In an effort to improve local disease control and oncologic outcomes after liver ablation, several factors have been studied (15-19). Among the known factors associated with improved local tumor control with ablation, lesion diameter < 3 cm, number and location of tumors, and minimal ablation margins achieved around the target tumor(s) are widely recognized as critical variables, with the latter being the only one passive for modification during treatment delivery. Moreover, it has been recently described that biological factors such as the RAS mutational status are also prognostic indicators for local recurrence and survival in patients undergoing ablation of CLM and have prompted recommendations for wider ablation margins in patients with RAS-mutated tumors (8, 20), suggesting that the minimal ablation margin acceptable for optimal disease control needs to be tailored to distinct tumor subtypes.

In order to provide adequate ablation margins, several elements are important: firstly, it is critical to have optimal definition of the tumor extent on intra-procedural CT

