image; secondly, confirmation of precise probe placement in relation to the tumor is needed intra-procedurally; thirdly, the volumetric loss and peri-tumoral tissue inflammation promoted by the ablation limits the ability to evaluate with confidence the ablation margin intra-procedurally, therefore requiring a magnetic resonance (MR) or computed tomography (CT) study to be performed within 1-2 months following ablation procedure, a long period to evaluate the primary efficacy of this modality. Taking all together, those factors points to the need of having improved intra-procedurally imaging assessment of patients undergoing percutaneous ablation.

Currently, there are no commercially available tools that provide a robust and accurate method for tumor mapping and ablation confirmation that takes in consideration the biomechanical conformational changes promoted by this therapy. We hypothesize that local tumor control following percutaneous ablation of liver cancers will be significantly improved with the application of a dedicated anatomical linear elastic biomechanical model for treatment guidance and efficacy assessment by enabling the operator to accurately identify the tumor for ablation probe placement and assess intra-procedurally the minimal ablation margins, therefore increasing efficacy of percutaneous ablation therapy, ultimately improving liver progression-free survival rates.

Our preliminary data shows that our biomechanical model can accurately map the tumor, defined on pre-treatment computed tomography (CT) imaging, onto an intra-procedural CT image and is insensitive to imaging artifacts associated with ablation probe. We hypothesize that our innovative approach to modeling the tissue changes related to the ablation procedure will enable intra-procedure monitoring of the ablation

margin relative to the tumor. In addition, the combination of these technologies will provide further detailed information on the relationship between progression-free survival local tumor progression-free survival (LTPFS) and the ablation margins achieved.

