1.8 Method

RayStation® is a flexible, innovative treatment planning system. It combines unique features like unmatched adaptive therapy capabilities, multi-criteria optimization,

optimization for HDR brachytherapy and external beam therapy with photons, electrons, protons as well as helium and carbon ions. RayStation supports a wide range of treatment machines, providing one control center to create biomechanical deformable registrations using “Morpheus”. Morpheus lets the investigators focus all their skill and experience on evaluating and refining plan quality.

To investigate the impact of the proposed biomechanical model on clinical decisions during ablation guidance and end-point assessment, patients will be randomized in two treatment arms (i.e. experimental arm - including anatomical modeling of the liver, and control arm) with a 1:1 ratio. The primary objective is to assess whether applying biomechanical models during percutaneous ablation will increase the minimal ablation margins, which will be evaluated at the end of the procedure with the proposed software on both cohorts. Additionally, two other distinct end-points will be analyzed: ability of the model to provide tumor identification for ablation probe placement on intra-procedural non-contrast enhanced CT, and local tumor control rates achieved with the clinical application of this model. Operating physicians will be informed in respect which arm the patient was randomized at the time of ablation (figure 3).

[figure not shown]

Figure 3: Patient randomization flowchart

A. Impact on tumor targeting

The clinical trial will be designed according to the optimized parameters from our retrospective analysis. The optimized biomechanical models will be used to assess the accuracy (e.g. the ability of the model to accurately describe the motion, deformation, and volume change and tumor location in the liver between the pre-ablation contrast-enhanced CT and the intra-procedural non-contrast enhanced CT) in both cohort of patients. For the control arm, no information in respect tumor location and targeting will be provided for the operating physician during ablation. Imaging processing using the biomechanical model will be performed after procedure completion. For the experimental

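### The only between-arm test named for LTPFS adjusts for achieved ablation margin, so its arm hazard ratio is not the total effect of assignment

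*Combined protocol and SAP*

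**What the plan says.** Section 1.2 sets the question: "To assess whether applying the proposed method during percutaneous ablation improves local tumor progression-free survival (LTPFS) rates". Section 1.8, part C, adds the hypothesis that local control at 2 years will be better than in the control arm. Statistical Design says that the two arms will be compared on oncological outcomes.

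Statistical Methods, A. Analysis Plan, then names three things for LTPFS:

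- Kaplan-Meier estimates for each arm, with intervals for the quantiles.
- Time-point probabilities such as 2-year LTPFS, with pointwise 95% intervals.
- One multivariable Cox model "with ablative margin as a continuous variable to assess the significance of study arm and ablative margin size on LTPFS", which also adjusts for known covariates that are not enumerated there.

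No log-rank test, Cox model without margin, or test of the 2-year difference is named. Intra-hepatic progression-free survival (PFS) and overall survival (OS) are to be analysed in a similar way, without further detail.

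On the role of margin, section 1.4 lists it among the factors linked to local control, "with the latter being the only one passive for modification during treatment delivery". It describes the software as letting the operator "assess intra-procedurally the minimal ablation margins, therefore increasing efficacy of percutaneous ablation therapy". Section 1.8 says that margin is evaluated at the end of the procedure in both arms, and that the experimental-arm operator uses it to decide on further ablation. The Analysis Plan makes it the primary endpoint.

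**The concern.** The objective concerns the total effect of assignment to software guidance. A model that holds achieved margin fixed asks something else: whether the arms differ among patients with the same measured margin. Because margin follows randomisation and is meant to be changed by the intervention, putting it in the model takes out some or all of the benefit that the software is meant to produce.

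At stake is how the result will be read. A report could show Kaplan-Meier curves that separate, beside an arm hazard ratio near 1 from the only named test, and a reader could conclude that the software does nothing for local control. The wording for intra-hepatic PFS and OS leaves it unclear whether the same problem carries over.

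**Working it through.** **1. The plan's own figure.** Number of Participants gives 50 evaluable subjects per arm, a difference of 1.132 mm (2 v 3.132), SD 2, two-sided 0.05 and 80% power. Noncentral-t power at 50 per arm is 80.0%, and 50 is the smallest number that reaches 80%. It reproduces. The plan gives no power figure for LTPFS.

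**2. Inputs.** From the documents: margins 2.0 and 3.132 mm, SD 2; local recurrence 20% to 45% (section 1.8, part C, no time point given); software error 3 mm (section 1.8, part B). Assumed, because the documents give no value: hazard ratio 0.6 to 0.9 per mm of true margin; margin error SD 0, 1.0 or 1.5 mm (1.5 reads the 3 mm as 2 SD); 2-year mortality 0 or 20%, unrelated to margin.

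**3. Total effect if margin is the only route.** Arm hazard ratio ≈ (hazard ratio per mm)^1.132. Large-sample Cox fits with arm only, over progression of 20, 30 and 45%, give:

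| HR per mm | Formula | Fits, no deaths | Fits, 20% mortality |
|---|---|---|---|
| 0.6 | 0.56 | 0.57-0.62 | 0.70-0.80 |
| 0.7 | 0.67 | 0.67-0.70 | 0.77-0.84 |
| 0.8 | 0.78 | 0.77-0.79 | 0.84-0.89 |
| 0.9 | 0.89 | 0.88-0.90 | 0.92-0.95 |

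**4. With margin in the model.** The share of the arm log hazard ratio that stays on the arm term is approximately

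error variance / variance of measured margin.

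- Error SD 0: 0%. Fitted arm hazard ratio 0.99-1.02.
- Error SD 1.0: 1/4 = 25% if the SD of 2 mm already contains the error; 1/(4 + 1) = 20% if it does not.
- Error SD 1.5: 2.25/4 = 56% if it does; 2.25/(4 + 2.25) = 36% if it does not.

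Large-sample fits agree: 21-29% and 53-61% under the first reading of the SD, 20-22% and 37-40% under the second. Number of Participants does not say which reading applies. At 0.6 per mm and error SD 1.5, the arm hazard ratio with margin in the model is about 0.72 under the first reading and 0.83 under the second.

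**5. Power for LTPFS.** Over the assumed scenarios (first reading of the SD), with 50 per arm, the log-rank test rejects in 4.5% to 35.7% of simulated trials. The arm term with margin in the model rejects in 3.5% to 15.4%.

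**6. Interim rule.** Number of Participants says "We will stop enrollment at the control arm at our interim look if our p-value is less than 0.003" and "The next 50 patients would be enrolled on the experimental arm only". With 25 per arm the noncentrality is 1.132/(2 × √(2/25)) = 2.00, so the probability of two-sided p < 0.003 is 14.5% under the design assumptions. The later patients would then not be randomised. With 25 per arm, log-rank rejection is 4.4% to 20.3%.

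**The case against.** **The unadjusted contrast is already there.** Objective 1 speaks of rates, and the plan reports Kaplan-Meier curves and 2-year LTPFS by arm, none conditioned on margin. This stands in part: a reader might infer that the plan offers no unadjusted view of the arms, and that is not so. But no between-arm test or contrast is attached to these estimates.

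**The margin model has its own purpose.** Section 1.4 also wants to learn about the relation between "local tumor progression-free survival (LTPFS) and the ablation margins achieved", and the plan never calls the arm coefficient the total effect. This stands. The model is legitimate for that aim; the gap is that nothing else tests the arms.

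**The effect need not vanish.** A reader might infer that adjustment removes the whole benefit. That requires an error-free margin as the sole route. The documents state a 3 mm software error and a second possible route, "tumor identification for ablation probe placement on intra-procedural non-contrast enhanced CT".

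**The hazard ratio need not exceed 1.** A reader might infer that the adjusted result could reverse. Simulated values of 1.11-1.22 arose only when an assumed cause that lowers margin and raises hazard was left out; adding it returned the arm hazard ratio to 0.99-1.02. The documents give no evidence of such a cause beyond the factors already named. Tumor size, number and location in section 1.4 and the minimisation factors are obvious candidates for the unlisted covariates.

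**LTPFS is secondary and underpowered.** True, and it limits the severity. It does not justify testing a different quantity from the one the objective names.

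**Conclusion.** The concern holds. As written, the only named arm test for LTPFS estimates the arm difference at equal measured margin and does not answer secondary objective 1. That conclusion follows from the text and needs no assumed number.

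The size does rest on assumptions. With the plan's margins, 0.6 to 0.9 per mm, no deaths and an error-free margin as the only route, the arm hazard ratio is about 0.57-0.90 without margin and about 1.0 with it. Assumed mortality of 20% moves the first range to 0.70-0.95. With margin error SD 1.0 to 1.5 mm, roughly 20-60% of the log hazard ratio remains, depending on that SD and on whether the SD of 2 mm already includes the error. When the effect per mm is weak (0.9), the two models differ little.

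A reader might infer that the trial's main conclusion is at risk. It is not: the primary endpoint is margin itself, and its analysis is untouched. The harm is a misread secondary hazard ratio. This should be fixed before outcomes are analysed.

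**What to change.** In Statistical Methods, A. Analysis Plan:

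- Name as the arm comparison for LTPFS, intra-hepatic PFS and OS a log-rank test, with a hazard ratio and 95% CI from a Cox model that contains arm and not margin.
- If that model is adjusted, use only baseline covariates chosen in advance from the minimisation factors, their number in proportion to expected events, deaths included. Arm plus all factors is 1 + 3 (histology/RAS) + 2 (size) + 1 (subcapsular) + 1 (multiplicity) = 8 parameters. The simulated trials averaged 16-43 events without deaths and 33-55 with 20% mortality, or 2.0-5.4 and 4.1-6.9 per parameter. Whether to stratify the test, and exactly how many factors to use, is the sponsor's choice.
- Keep the Cox model with margin as a separate analysis of how margin relates to LTPFS, and state that its arm coefficient is not the treatment effect.
- State that if the interim rule closes the control arm, the comparison uses concurrently randomised patients only.

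The cost is a few sentences and one extra model fit per endpoint, with no new data. The change corrects what is estimated; it does not raise power, which stays low, so the hazard ratio should be read with its interval.
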